8.4.1.2 Visit Windows for Pediatric Stage 2 Rollover Participants

For participants rolling from Pediatric Stage 1 into Pediatric Stage 2, the visit windows are defined below:

- Total Screening Period:
 - Up to 28 days from the Stage 1 Study Follow-up Visit at which negative, suboptimal or low immune response to the previous COVID-19 vaccine was obtained until the S2 Baseline/Week 0 visit.
 - If the S2 Baseline/Week 0 visit cannot be conducted within 28 days of the qualifying Stage 1 Follow-up Visit noted above, the participant will return to the site for a full S2 Screening visit, as described in Section 8.4.2.3.2 Screening for Pediatric Stage 2 Rollover Participants.
 - S2 Screening Phone Visit: at least 7 days prior to administration of the alternative vaccine at S2 Baseline/Week 0.
 - See Section 8.4.2.3.2 Screening for Pediatric Stage 2 Rollover Participants for more details on the screening procedures for rollover participants
- S2 Baseline (S2 Week 0/Day 1)
 - See Section 8.2.4 Baseline (Week 0/Day 1) Visit for more details on the S2 Baseline/Week 0 visit activities.
- S2 Week 1: Vaccine Diary Review Phone Visit (Day 8 – Day 12)
- S2 Week 4: (+/- 1 week)
- S2 Week 12: (+/- 2 weeks)
- S2 Week 24: (+/- 2 weeks)
- S2 Week 36: (+/- 2 weeks)
- S2 Week 48 (End of Study): (+/- 2 weeks)

8.4.2 Screening and Allocation

8.4.2.1 Pre-Screening

8.4.2.1.1 Pre-Screening for Pediatric Stage 2 Newly Recruited Participants

An optional Pre-Screening visit may be conducted to confirm that a participant has had a negative, suboptimal, or low immune response to initial COVID-19 vaccine regimen prior to Screening. This study will be explained in lay language to each potential participant. Each participant will sign an informed consent form before committing to study Pre-Screening procedures. Pre-Screening procedures at the study site will vary by method of recruitment as outlined below:

Study site personnel are responsible for the following:

1. Consent the participant for an ACV01 Pre-Screening Evaluation.
2. Conduct the rapid result or other antibody testing.
3. Invite the participant to an ACV01 Screening Visit if the result is negative or weakly positive per the site preferred antibody test method.

8.4.2.1.2 Pre-Screening for Pediatric Stage 2 Rollover Participants

Elecsys® Anti-SARS-CoV-2 S assay results for Stage 1 participants from visits at Week 4 through Week 48 will be reviewed when received by study sites. Participants with a negative, suboptimal, or low immune response at any visit following receipt of the previous COVID-19 vaccine dose will have the data from their last Stage 1 study visit pre-screened to determine if they may qualify for Stage 2.

If a participant pre-screens successfully for Stage 2, the study site will contact the participant to offer them the opportunity to be fully screened for Stage 2.

8.4.2.2 Determination of Participant Cohort and Identification of Qualifying Disease

Prior to screening a potential newly recruited participant, the site needs to determine to which IS cohort the participant will be allocated and identify the participant's qualifying autoimmune disease.

Note that the qualifying disease for rollover participants will be the same as for Stage 1.

Cohorts: Stage 2 will be accepting participants who are taking 3 types of IS medications: MMF or MPA, MTX, and B cell depletion therapies. The criteria for allocation to each cohort are listed below:

- Cohort D: Receipt of MMF or MPA (\pm other rheumatic disease medications, including biologics)
 - Participants who are taking MMF or MPA will be placed in this cohort.
 - Participants may not also be taking MTX.
 - Participants may not have taken anti-CD20 and anti-CD19 B cell depleting therapy in the past 18 months.
- Cohort E: Receipt of MTX (\pm other rheumatic disease medications, including biologics)
 - Participants who are taking MTX will be placed in this cohort.
 - Participants may not also be taking MMF/MPA.
 - Participants may not have taken anti-CD20 and anti-CD19 B cell depleting therapy in the past 18 months.
- Cohort F: Receipt of anti-CD20 or anti-CD19 B cell depletion therapy within the past 18 months (\pm other rheumatic disease medications)
 - Participants who have taken B cell depletion medications in the past 18 months will be placed in this cohort.
 - Participants may also be taking MMF/MPA or MTX.

Qualifying Autoimmune Diseases: The ACV01 study will be accepting participants diagnosed with SLE, JIA, JDM, or POMS. In the event that a participant has more than one of these 4 diseases, disease activity assessments will be collected throughout the trial for only the disease associated with IS medication cohort assignment at entry into the trial.

8.4.2.3 Screening

8.4.2.3.1 Screening for Pediatric Stage 2 Newly Recruited Participants

The research study will be explained in lay terms to each potential pediatric participant and his or her parent/guardian. The potential participant and their parent/guardian will sign IRB-approved informed consent and assent forms, as appropriate to the age of the participant, before undergoing any study procedures. Once the informed consent/assent forms have been signed, the participant will be assigned a unique participant number. At this time, study-specific procedures may be performed.

The purpose of the screening period, which begins at the time of signed consent, is to confirm eligibility to enter the study. All screening procedures, assessments, and laboratory measures to determine participant eligibility will be conducted within a 21-day screening window with shorter time periods expected for most participants.

The assessment of eligibility may take a series of visits that occur on separate days. The Screening visit biomarkers should reflect, as much as possible, the biometrics of the participant prior to any study procedures.

The following procedures, assessments, and laboratory measures will be conducted:

1. Informed Consent/Accent
2. Demographics
3. Medical History
4. Concomitant Medications (including contraceptives)
5. Comprehensive Physical Exam
6. Vital Signs
7. Confirmation of Disease Classification Criteria Assessment
 - a. 2017 EULAR/ACR classification criteria for adult and juvenile idiopathic inflammatory myopathies and their major subgroups for pediatric SLE
 - b. 2010 ILAR classification criteria for JIA
 - c. 2017 McDonald diagnostic criteria for MS
 - d. Bohan and Peter criteria or the 2017 EULAR/ACR classification criteria for JDM.
8. Complete assessments of disease activity: SLEDAI-2K for pediatric SLE; Tender/Swollen Joint Count for JIA; Physician-assessed relapse for POMS; Flare Assessment for JDM and CMAS for JDM
9. Review of COVID-19 vaccination record and antibody responses, infections and treatments.
10. Central laboratory assessments for all participants
 - a. Elecsys® Anti-SARS-CoV-2 S assay to assess response to initial COVID-19 vaccine regimen
 - b. CBC with differential
 - c. CMP, eGFR
11. Local laboratory assessments for all participants
 - a. Molecular COVID-19 Testing
 - b. Urine pregnancy test (postmenarcheal females must have a negative urine pregnancy test at Screening)
12. Disease-specific laboratory assessments:
 - a. Pediatric SLE participants only
 - i. Anti-dsDNA, C3, C4
 - ii. Random urine protein-creatinine ratio
 - iii. Urinalysis (microscopic)
 - iv. Erythrocyte sedimentation rate (ESR) – local assessment
 - b. JIA participants only
 - i. CRP
 - c. B-cell depleting therapy participants only

- i. If on CD20 depleting agent, CD19+ B cells
- d. JDM participants only
 - i. Disease-specific tests assessed as part of the CMP:
 - 1. Creatine kinase (CK) only
 - 2. Alanine aminotransferase (ALT)/aspartate aminotransferase (AST)
 - ii. Aldolase

13. Inclusion/Exclusion criteria assessment

Participants with abnormal laboratory values that prohibit entry may be re-tested once during the screening period, which may last up to 21 days. Participants who screen fail may be rescreened one time and must repeat all screening assessments. Any further rescreening activity requires approval by the medical monitor.

During the Screening visit, the site will review vaccine eligibility criteria, per Section 8.4.4 Baseline (Week 0/Day 1) Visit with the participant.

8.4.2.3.2 Screening for Pediatric Stage 2 Rollover Participants

The study site will contact potential Stage 2 rollover participants to offer them the opportunity to be fully screened for Stage 2. There are two options for the conduct of the full Screening for Pediatric Stage 2 for rollover participants:

- The screening process for Stage 2 may be able to be completed with only a telephone visit if the necessary information is available from the last study visit from Stage 1, informed consent can be appropriately completed, etc.
 - *Notes:*
 - *Information that may be available from the last study visit from Stage 1 includes lab tests for eligibility and disease-specific laboratory tests noted below.*
 - *The pregnancy test and molecular COVID-19 tests do not need to be completed during the Stage 2 Screening period if the Screening visit is conducted by phone. In such cases, these assessments will be conducted at the beginning of the Stage 2 Baseline visit before the vaccine is administered.*
- If the needed data are not available from the previous Stage 1 visit or 28 days will have passed when the S2 Baseline/Week 0 visit is reached, then the Stage 2 Screening visit must be conducted at the clinical site.

The following procedures, assessments, and laboratory measures will be conducted to determine participant eligibility for Stage 2.

1. Confirm that participant agrees to proceed to Stage 2.
 - a. If the participant has not yet signed an informed consent/assent form that includes a description of Stage 2, the participant must provide signed informed consent for Stage 2 screening to proceed.
2. Updated Medical History
3. Updated Concomitant Medications (including contraceptives)
4. Updated Physical Exam
 - a. Results of the Targeted Physical Exam and the Neurological Exam from the most recent Stage 1 visit may be used to fulfill this assessment in place of a new Comprehensive Physical Exam
5. Vital Signs
6. AE assessment following vaccination in Stage 1

7. Complete assessments of disease activity: SLEDAI-2K for pediatric SLE; Tender/Swollen Joint Count for JIA; Physician-assessed relapse for POMS; Flare Assessment for JDM and CMAS for JDM

8. Response to previous COVID-19 vaccine dose assessed by Elecsys® Anti-SARS-CoV-2 S assay

9. Central laboratory assessments for all participants

a. Elecsys® Anti-SARS-CoV-2 S assay to assess response to previous COVID-19 vaccine dose

b. CBC with differential

c. CMP, eGFR

10. Local laboratory assessments for all participants

a. Molecular COVID-19 Testing (if Stage 2 Screening visit is conducted at the clinical site only)

b. Urine pregnancy test (if Stage 2 Screening visit is conducted at the clinical site for women of child-bearing potential only)

11. Disease-specific laboratory assessments:

a. Pediatric SLE participants only

i. Anti-dsDNA, C3, C4

ii. Random urine protein-creatinine ratio

iii. Urinalysis (microscopic)

iv. Erythrocyte sedimentation rate (ESR) – local assessment

b. JIA participants only

i. CRP

c. B-cell depleting therapy participants only

i. If on CD20 depleting agent, CD19+ B cells

d. JDM participants only

i. Disease-specific tests assessed as part of the CMP:

1. Creatine kinase (CK) only

2. Alanine aminotransferase (ALT)/aspartate aminotransferase (AST)

ii. Aldolase

12. Inclusion/Exclusion criteria assessment

8.4.3 Evaluation of Eligibility and Allocation

If the participant meets all eligibility criteria for Stage 2, then proceed as follows during the Screening phone call:

- Allocate the participant to the appropriate cohort based on IS medication
- Schedule S2 Baseline/Week 0 visit (within 28 days of the Stage 2 Screening assessments and no sooner than 7 days from the Screening visit).
- Communicate to the participant the details of the medication hold to the participant per Section 7.1.1 Protocol-mandated Medications.
- Inform the participant that there should be no changes to his/her other existing medications between Screening and the S2 Baseline/Week 0 visit.

8.4.4 Baseline (Week 0/Day 1) Visit

Eligible participants who meet all inclusion criteria and none of the exclusion criteria for Stage 2 will proceed with visits and assessments according to Section 20.1 Schedule of Events, [Table 21](#) (newly recruited participant) or [Table 22](#) (rollover participant). Eligible participants will be assessed for disease activity and SARS-CoV-2 infection at the S2 Baseline/Week 0 visit, prior to receipt of an alternative vaccine dose. Prior to administering the alternative vaccine dose at the Baseline visit, the site will confirm the participant meets vaccine eligibility per the criteria below:

- No increase to the permitted concomitant medications in participants in Cohorts D and E between S2 Screening and S2 Baseline/Week 0.
- No B-cell depletion infusions or changes in permitted concomitant medications in participants in Cohort E between allocation and S2 Baseline/Week 0.
- No clinically active disease (including myocarditis or pericarditis) at S2 Baseline/Week 0 resulting in an increase/addition of IS medications. For participants with MS, no suggestion of a MS relapse per the investigator.
- No active myocarditis or pericarditis based on review of clinical symptoms.
- No positive molecular COVID-19 test at S2 Baseline/Week 0.
- No increase in oral, intramuscular, or intravenous steroids within 14 days of S2 Baseline/Week 0.

If the vaccine cannot be administered at the S2 Baseline Week 0 visit, it must be administered during the following 2-3 days. Vaccine eligibility will be confirmed prior to administration of the vaccine. **Administration of the alternative vaccine dose must occur within 28 days of the S2 Screening visit (newly recruited participant) or 28 days of when the data used for screening were obtained (rollover participant).**

If a **newly recruited participant** is not eligible to receive the alternative vaccine dose at S2 Baseline Week 0, he/she will be terminated from the study (see Section 11.2 Participant Stopping Rules and Withdrawal Criteria), and the participant will be replaced. If a **rollover participant** is not eligible to receive the alternative vaccine dose at S2 Baseline Week 0, he/she will continue on the previous Schedule of Events.

The participant may rescreen after 30 days from determination of vaccine ineligibility. New recruit participants who fail to receive the vaccine must be rescreened under a new participant ID. Participants who are not eligible to receive an alternative vaccine dose at that visit may restart their IS medications immediately.

See Section 8.3.4 Study Procedures and Assessments for more information on individual clinical and research assessments.

Sites will call all Stage 2 participants who withheld an IS medication after the S2 Baseline visit to provide instructions on resuming IS medication per Section 7.1.1 Protocol-mandated Medications.

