8.1.3 Baseline (Week 0/Day 1) Visit

Eligible participants who meet all inclusion criteria and none of the exclusion criteria will proceed with visits and assessments according to Section 20.1 Schedule of Events. Eligible participants will be assessed for disease activity and SARS-CoV-2 infection at the Baseline/Week 0 visit, prior to receipt of an additional homologous vaccine dose. Prior to administering the additional homologous vaccine dose at the Baseline visit, the site will confirm the participant meets vaccine eligibility per the criteria below:

- No increase to the permitted concomitant medications in participants in Cohorts A and B between Randomization and Baseline/Week 0.
- No B-cell depletion infusions or changes in permitted concomitant medications in participants in Cohort C between allocation and Baseline/Week 0.
- No clinically active disease (including myocarditis or pericarditis) at Baseline/Week 0 resulting in an increase/addition of IS medications. For participants with MS, no suggestion of a MS relapse per the investigator.
- No active myocarditis or pericarditis based on review of clinical symptoms.
- No positive molecular COVID-19 test at Baseline/Week 0.
- No increase in oral, intramuscular, or intravenous steroids within 14 days of Baseline/Week 0.

If the vaccine cannot be administered at the Baseline/Week 0 visit, it must be administered during the following 2-3 days. Vaccine eligibility will be confirmed prior to administration of the vaccine. **Administration of the additional homologous vaccine dose must occur within 28 days of the Screening visit.**

If a participant is not eligible to receive the additional homologous vaccine dose at Baseline/Week 0, he/she will be terminated from the study. The participant may rescreen under a new participant ID after 30 days from the determination of vaccine ineligibility. Participants who were randomized to withhold cohort-defining IS medications before the Baseline visit and who are not eligible to receive an additional homologous vaccine dose at that visit, may restart their IS medications immediately. The participant will be replaced.

See Section 8.1.4 Study Procedures and Assessments for more information on individual clinical and research assessments.

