8.2.4 Baseline (Week 0/Day 1) Visit

Eligible participants who meet all inclusion criteria and none of the exclusion criteria for Stage 2 will proceed with visits and assessments according to Section 20.1 Schedule of Events, [Table 18](#) (newly recruited participant) or [Table 19](#) (rollover participant). Eligible participants will be assessed for disease activity and SARS-CoV-2 infection at the S2 Baseline/Week 0 visit, prior to receipt of an alternative vaccine dose. Prior to administering the alternative vaccine dose at the Baseline visit, the site will confirm the participant meets vaccine eligibility per the criteria below:

- No increase to the permitted concomitant medications in participants in Cohorts D and E between S2 Screening and S2 Baseline/Week 0.
- No B-cell depletion infusions or changes in permitted concomitant medications in participants in Cohort F between allocation and S2 Baseline/Week 0.
- No clinically active disease (including myocarditis or pericarditis) at S2 Baseline/Week 0 resulting in an increase/addition of IS medications. For participants with MS, no suggestion of a MS relapse per the investigator.
- No active myocarditis or pericarditis based on review of clinical symptoms.
- No positive molecular COVID-19 test at S2 Baseline/Week 0.
- No increase in oral, intramuscular, or intravenous steroids within 14 days of S2 Baseline/Week 0.

If the vaccine cannot be administered at the S2 Baseline Week 0 visit, it must be administered during the following 2-3 days. Vaccine eligibility will be confirmed prior to administration of the vaccine. **Administration of the alternative vaccine dose must occur within 28 days of the S2 Screening visit (newly recruited participant) or 28 days of when the data used for screening were obtained (rollover participant).**

If a **newly recruited participant** is not eligible to receive the alternative vaccine dose at S2 Baseline Week 0, he/she will be terminated from the study (see Section 11.2 Participant Stopping Rules and Withdrawal Criteria), and the participant will be replaced. If a **rollover participant** is not eligible to receive the alternative vaccine dose at S2 Baseline Week 0, he/she will continue on the previous Schedule of Events.

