8.4 Pediatric Stage 2 Study Procedures

8.4.1 Visit Windows

8.4.1.1 Visit Windows for Pediatric Stage 2 Newly Recruited Participants

Appendix 20.1, [Table 21](#) presents the Schedule of Events for participants who are newly recruited to Pediatric Stage 2.

The visit windows are defined below:

- Screening and Allocation: 28 to 7 days prior to the S2 Baseline/Week 0 visit.
- Baseline (Week 0/Day 1)
 - See Section 8.4.4 Baseline (Week 0/Day 1) Visit for more details on Baseline/Week 0 visit activities.
- Week 1: Vaccine Diary Review Phone Visit (Day 8 – Day 12)
 - Pediatric participants may consent to an optional mechanistic specimen collection at Week 1. If the participants have consented to this mechanistic specimen collection, the Vaccine Diary Review will occur on site per the assessments outlined in Section 20.1 Schedules of Events, [Table 21](#).

- Week 4: (+/- 1 week)
- Week 12: (+/- 2 weeks)
- Week 24: (+/- 2 weeks)
- Week 36: (+/- 2 weeks)
- Week 48 (End of Study): (+/- 2 weeks)

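### Protocol Section 8.4.4 names Cohort E (methotrexate) where it should name Cohort F (B-cell depletion), so the Pediatric Stage 2 pre-dosing list does not bar a routine scheduled infusion in a newly recruited Cohort F child

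*Protocol*

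**What the plan says.** Protocol Section 8.4.4 lists the conditions a site must confirm before giving the alternative dose in Pediatric Stage 2. Two of them concern medication and are specific to a cohort. One reads "No increase to the permitted concomitant medications in participants in Cohorts D and E between S2 Screening and S2 Baseline/Week 0". The next reads "No B-cell depletion infusions or changes in permitted concomitant medications in participants in Cohort E between allocation and S2 Baseline/Week 0". Neither mentions Cohort F.

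The corresponding condition for Adult Stage 2 (Section 8.2.4) is "No B-cell depletion infusions or changes in permitted concomitant medications in participants in Cohort F between allocation and S2 Baseline/Week 0". For Stage 1 (Section 8.1.3, which Section 8.3.3 also applies to children) it is "No B-cell depletion infusions or changes in permitted concomitant medications in participants in Cohort C between allocation and Baseline/Week 0".

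Newly recruited children are directed to Section 8.4.4 twice. Section 8.4.1.1 says "See Section 8.4.4 Baseline (Week 0/Day 1) Visit for more details on Baseline/Week 0 visit activities", and Section 8.4.2.3.1 says "During the Screening visit, the site will review vaccine eligibility criteria, per Section 8.4.4 Baseline (Week 0/Day 1) Visit with the participant". If such a child fails the list, Section 8.4.4 provides that "he/she will be terminated from the study (see Section 11.2 Participant Stopping Rules and Withdrawal Criteria), and the participant will be replaced". The child may rescreen after 30 days under a new participant ID.

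**The concern.** The restriction sits on a cohort where it has practically nothing to act on and is missing from the cohort it was written for. For Cohorts D and E, Section 8.4.2.2 states: "Participants may not have taken anti-CD20 and anti-CD19 B cell depleting therapy in the past 18 months". Children on depletion therapy go to Cohort F.

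This is an operative check made immediately before dosing, not background text. The Protocol itself associates B-cell depletion with poor vaccine response (Sections 1.1 and 1.2.1), so an infusion shortly before the dose bears on the Week 4 antibody result in the two pediatric Cohort F arms. A site applying Section 8.4.4 literally could dose a child whom the intended rule would have withdrawn and replaced. That child would enter the vaccinated population. Because no listed condition was breached, the infusion might not be recorded as a deviation, and the child could then stay in the per-protocol replicate as well.

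**Working it through.** The plan gives no figure to reproduce here; the check is a comparison of text.

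**1. The three parallel lists**

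| Population | Section | First medication bullet | Infusion bullet | Depletion cohort |
|---|---|---|---|---|
| Stage 1 | 8.1.3 | A and B | C | C |
| Adult Stage 2 | 8.2.4 | D and E | F | F |
| Pediatric Stage 2 | 8.4.4 | D and E | **E** | F |

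The pattern is one bullet for the two antimetabolite cohorts and one for the depletion cohort. Section 8.4.4 alone breaks it: E appears twice and F not at all. The cohort letters have the same meaning in Adult and Pediatric Stage 2 (Sections 3.1.1.2 and 3.1.2.2), and no design reason for a difference is given.

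**2. What other text already stops in a Cohort F child**

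- *Infusion given for active disease:* barred. The active-disease condition in Section 8.4.4 applies to every cohort, and exclusion 5 for new recruits (Section 4.2.2.2.1.2) covers the Screening period.
- *Newly added infusion, or a changed dose or frequency:* barred by Section 7.1.2 between allocation and Baseline.
- *Infusion already scheduled, at its usual dose and interval:* not expressly barred. It is not an addition or a change. The instruction in Section 8.4.3 not to change other existing medications has the same limit. For Cohort C in Stage 1, Section 7.1.1 expects prescribed depletion therapy to continue.

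Only the third case remains.

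**3. Who is exposed**

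Newly recruited children are sent to Section 8.4.4. Rollover children are sent by Section 8.4.1.2 to Section 8.2.4, which names Cohort F, although Section 8.4.4 also describes itself as covering rollovers. The exposure is therefore mainly in new recruits.

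**4. Size**

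- Arms concerned: F1P and F2P (Table 9). Capacity is 2 × 80 = 160 places of 6 × 80 = 480, and 160 / 480 = 33%. This counts places, including any filled by rollovers. It does not count affected children.
- Window: 7 to 28 days before S2 Baseline (Sections 8.4.1.1 and 8.4.3).
- Not available: the number of new recruits, the interval between infusions, and the effect of an infusion on the Week 4 response. No event count or bias can be calculated.

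**5. Analysis populations**

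Under Protocol Section 13.4.1 and SAP Section 5, a dosed child is in the vaccinated population. Apart from adherence to the immunosuppressant plan, per-protocol exclusion requires a major deviation or an unmet entry criterion that would affect the Week 4 assessment. Recording a deviation is not sufficient; it has to be classed as major and as affecting that response.

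**The case against.** The strongest reply is that this is a one-letter error that a competent site would see through, since an infusion bar on a cohort without depletion therapy makes little sense. The Protocol also leads to the right text by more than one route. Section 8.4.1.2 sends rollovers to Section 8.2.4. Section 8.4.4 refers to Section 11.2, whose item 5 cites the Section 8.2.4 criteria for Stage 2 new recruits.

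Most of this stands as evidence of intent, and it makes misapplication less likely. It does not correct the list. Item 5 of Section 11.2 gives reasons for withdrawal and is not a dosing check, and it omits Section 8.4.4. Section 6.7 points to Section 8.1.3, which names Cohort C. A newly recruited child is still governed by a list without the restriction.

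A reader might infer more than the documents support:

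- *That pediatric Cohort F has no protection against infusions before dosing.* It has; only the routine scheduled infusion escapes.
- *That a third of Pediatric Stage 2 is affected.* The 33% is the capacity of two arms.
- *That Cohort E is materially disadvantaged by having a no-change condition added to its no-increase condition.* Sections 7.1.2 and 8.4.3 already tell all these participants not to change medication. The bullet makes that instruction a dosing condition for Cohort E, but no numerical effect follows.

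**Conclusion.** The cohort label in Section 8.4.4 is wrong and should be F. The practical consequence is narrow: a newly recruited Cohort F child (arms F1P, F2P) with a routine, already scheduled depletion infusion between allocation and Baseline passes the pediatric list, while an adult in the same position would be ineligible for the dose under Section 8.2.4.

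The effect is confined to Stage 2 secondary objectives (Section 2.2.2). The primary objective concerns the homologous dose (Section 2.1) and is not touched, so a reader should not infer that the primary result is at risk. Nor do the documents support a claim of bias of any stated size in the Stage 2 response rates.

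The conclusion rests on two readings: that an infusion at its usual dose and interval is not a medication change under Sections 7.1.2 and 8.4.3, and that sites apply Section 8.4.4 as written to new recruits.

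**What to change.** - In the infusion condition of Section 8.4.4, replace Cohort E with Cohort F.
- In Section 8.4.1.2, point rollover children to Section 8.4.4, and add Section 8.4.4 to item 5 of Section 11.2, so that all Pediatric Stage 2 participants are held to one list.
- Notify sites.
- State in the Protocol or SAP that, for any Cohort F child infused between allocation and vaccination and still dosed, the infusion is classed as a major deviation affecting the Week 4 response. The existing per-protocol definition then excludes the child. The statement is needed because a child dosed under the uncorrected list did not breach it, so it is unclear whether the infusion would count as a deviation under Section 16.1. The vaccinated population stays as defined.

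The text changes are one letter, two cross-references and one sentence. They need IRB approval before use (Section 17.1), and the investigator's statement at the front of the Protocol also requires written permission from the IRB and NIAID. They can go into the next amendment. No new data are needed: Section 13.4.5 collects all medications throughout the study, and SAP Section 6.2 already summarizes time from last depletion dose to vaccine in Cohort F.
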